3. DESCRIPTION OF DESIGN AND TRIAL POPULATION

3.1 OVERALL TRIAL DESIGN AND PLAN

This open label long term extension trial investigates the long term safety and efficacy of BI 655066/ABBV-066 (risankizumab). Approximately 60 patients who meet the entry criteria are planned for inclusion in this trial, rolling over from preceding trial 1311.6. The treatment will be open label.

The treatment period will be 204 ([Flow chart 1](#)), 206 ([Flow chart 2](#)) or 216 ([Flow chart 3](#)) weeks, followed by a 140 day follow up period.

Patients rolling over from preceding trial 1311.6 will have to complete period 2 or 3 in that trial and either demonstrate a clinical response without remission at Visit E1 or a clinical response or remission at Visit E5 as defined by that protocol (see Figure 3.1:1).

[figure not shown]

Figure 3.1:1 Guideline for roll over of patients from 1311.6 to long term extension study 1311.20/M15-989

All patients directly rolled over from 1311.6 into 1311.20/M15-989 will receive 180 mg BI 655066/ABBV-066 (risankizumab) subcutaneously from visit 2 onwards every

8 weeks, until the EoT visit is performed. Patients who complete this study may elect to continue in M16-000 Sub-Study 3 (Phase 3 open label extension study).

Patients who have completed 1311.6 qualifying for roll-over into 1311.20/M15-989 before availability of this study, can be enrolled depending on their clinical remission or response. If patients were treated between finishing 1311.6 and entering 1311.20/M15-989 with anti-TNF therapy or any biologic agent an 8 weeks or 5 times the half-life (whichever is longer), wash-out period will be needed before administration of first i.v or s.c. study medication. Patients must maintain their best response status (clinical response or remission) post 1311.6. Patients who dropped from 1311.6 with remission must maintain remission or undergo re-induction while responders will have to maintain their response.

- If clinical response or remission (CDAI drop >100 from baseline of 1311.6 or CDAI < 150) was maintained after end of treatment and is confirmed at screening for 1311.20/M15-989, patients can directly be assigned to open label s.c. maintenance treatment with 180 mg every 8 weeks (FLOW CHART 1) (visit window between last IMP dose in 1311.6 and first IMP dose in 1311.20/M15-989 should be at least 8 weeks).
- If clinical remission (achieved at E5 1311.6) has been lost after end of treatment in 1311.6 and/or at screening for 1311.20/M15-989, patients will receive open label i.v. re-induction treatment with three infusions of 600 mg each every 4 weeks after which eligibility will be re-assessed. If clinical remission or at least response compared to 1311.6 study baseline (V2) is achieved patients will switch to s.c. maintenance treatment with 180 mg s.c. every 8 weeks ([Flow chart 3](#)), otherwise an EoT visit has to be performed. After last administration of trial drug in 1311.20/M15-989 trial, a 140 day follow up call should be scheduled for patients who do not elect to enroll in Study M16-000.
- If clinical response (achieved at E1 or E5 1311.6) has been lost after end of treatment in 1311.6 and/or at screening for 1311.20/M15-989, patients will receive open label i.v. re-induction treatment with three infusions of 600 mg each every 4 weeks after which eligibility will be re-assessed. If clinical response or remission compared to 1311.6 study baseline (V2 1311.6) is achieved patients will switch to s.c. maintenance treatment with 180 mg s.c. every 8 weeks ([Flow chart 3](#)), otherwise an EoT visit has to be performed. After last administration of trial drug in 1311.20/M15-989 trial, a 140 day follow up call should be scheduled for patients who do not elect to enroll in Study M16-000.

The results from the last colonoscopy done in 1311.6 will serve as baseline for 1311.20/M15-989. A colonoscopy at screening is only required for patients who lost

response or remission during extended follow-up phase after completion of 1311.6. Colonoscopies are repeated once per year to assess the effect of continued treatment on endoscopic response and mucosal healing.

The end of study is defined as the date the last subject completes the End of trial visit

The primary analysis will be performed after all patients have completed their EoT visit. The reference values for the efficacy endpoints clinical or endoscopic response will be the baseline values in 1311.6.

For details regarding Adverse event and serious adverse event reporting, see [Section 5.2.2.2](#)

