Administration of trial s.c. medication ⁷	X	X	X	X	X	X	X	X	X	X	X

1. If an EoT colonoscopy has not been performed during E1/E5 within 1311.6, or if the patient had a treatment interruption followed by a clinical relapse, it must be performed between V1 and V2 in 1311.20/M15-989.
2. Assessments performed at visit E1/E5 in the previous trial do not have to be repeated at Visit 1 in this trial. Assessments scheduled but not performed at Visit E1/E5 in the previous trial should be repeated at visit 1 in this trial, and the results entered into the CRFs of both trials, 1311.6 and 1311.20/M15-989.
3. For patients who discontinue study medication before scheduled EoT visit, an early EoT visit should be performed. After last dose of study medication, a 140 day follow-up call should be scheduled. Upon EC/CA approvals of Study M16-000 protocol amendment 4, patients receiving treatment in M15-989 will have the option to enroll into M16-000 Sub-Study 3 after completing the EoT visit.
4. Must be performed at Visit 1 and starting from Visit 2 prior to each study drug administration in females of childbearing potential. In case of positive result, serum pregnancy test will be performed. Study drug will only be administered if pregnancy is ruled out.
5. Positive QuantiFERON-TB Gold In-Tube tests need not to be repeated. If TB or infection is suspected at any time during the study, a routine work up including chest x-ray and a QuantiFERON-TB Gold In-Tube test or an infection assessment must be performed at investigator's discretion and according to local guidelines.
6. Assessment of AE after intravenous infusions and subcutaneous injections will also include assessment of local tolerability. The assessment of local tolerability should be done just before the patient leaves the investigator site.
7. All assessments are to be completed prior to study drug administration, unless otherwise specified.
8. An end of trial call should be performed for both patients that agree to enroll into M16-000 Sub-Study 3 OLE or those that do not choose to participate.
9. For details of laboratory tests see [Section 5.2.3](#), [Table 5.2.3.1](#) and [Table 5.2.3.2](#).
10. Every effort should be made for the patient to perform a final ileocolonoscopy at the study visit where the last dose of study medication is administered. For patients with early EoT, every effort should be made to perform a final ileocolonoscopy within 2 weeks following the early EoT visit.

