4.3.2 Secondary Efficacy Endpoint

- Clinical remission by visit defined as a CDAI < 150.
- Clinical response by visit, defined by either a CDAI < 150 or a CDAI reduction from baseline of at least 100 points.
- PRO-2 remission by visit, defined by a PRO-2 score < 75
- PRO-2 response by visit, defined as a decrease from baseline of 50 points or more.
- CDEIS remission, defined as a score of 4 or less, by visit (for patients with initial isolated ileitis a score of 2 or less)
- CDEIS response, defined as a score of 7 or less, by visit (for patients with initial isolated ileitis > 50% reduction from baseline).

- Mucosal healing, using CDEIS defined as the absence of mucosal ulceration, i.e., ulceration sub-score (deep ulceration, superficial ulceration, ulcerated stenosis) is 0, by visit.
- Deep remission, defined as clinical remission and CDEIS remission by visit.
- IBDQ remission (IBDQ total score > 170 points) by visit.
- IBDQ response (increase in IBDQ total score > 16 points from baseline) by visit.
- Change from baseline in CDAI by visit.
- Change from baseline in PRO-2 scores by visit.
- Change from baseline in CDEIS by visit.
- Change from baseline in SES-CD by visit.
- Change from baseline in stool frequency (SF) by visit based on patient diary.
- Change from baseline in abdominal pain (AP) score by visit based on patient diary.
- Change from baseline in IBDQ total scores by visit.
- Change from baseline in IBDQ domain scores by visit.
- Change from baseline in hs-CRP by visit.
- Change from baseline in fecal calprotectin profile by visit.

Note: For the composite endpoints such as deep remission, please refer to Appendix 12.9 for detailed analysis convention.

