6.0 Analysis Conventions

6.1 Definition of Baseline

Efficacy analysis:

For efficacy analysis, the baseline is defined as the last measurement prior to the first dose of the study drug in the feeder Study M15-993 (1311.6).

Safety analysis:

For safety analyses, the baseline is defined as the last measurement prior to the first dose of risankizumab in the feeder Study M15-993 (1311.6).

Demographics and Baseline Characteristics:

For Demographics and Baseline Characteristics, the data will be from the baseline of the feeder Study M15-993 (1311.6).

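### Protocol 3.1 and SAP 6.1 name different endoscopic baselines, and no planned paired analysis shows change in CDEIS or SES-CD since entry to the extension

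*Protocol*

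**What the plan says.** Protocol 3.1 makes two statements about the endoscopic reference. The first is "The results from the last colonoscopy done in 1311.6 will serve as baseline for 1311.20/M15-989". Two short paragraphs below comes the second: "The reference values for the efficacy endpoints clinical or endoscopic response will be the baseline values in 1311.6". The second names response only; it does not mention change scores.

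Between the two, the protocol gives the purpose of the examinations: "Colonoscopies are repeated once per year to assess the effect of continued treatment on endoscopic response and mucosal healing".

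SAP 6.1 has one rule and no exception for endoscopy: "For efficacy analysis, the baseline is defined as the last measurement prior to the first dose of the study drug in the feeder Study M15-993". SAP 4.3.2 then lists "Change from baseline in CDEIS by visit" and the same for SES-CD. Protocol 5.1.1 also lists percentage change and 75% reduction in both scores. SAP 4.3.3 adds an SES-CD decrease of more than 50%.

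For patients who relapsed between the trials there is a further examination. Footnote 1 to Flow Chart 3 says that "if the patient had a treatment interruption followed by a clinical relapse, it must be performed between V1 and V2 in 1311.20/M15-989".

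**The concern.** For response, the protocol and SAP agree on the 1311.6 baseline. For change in CDEIS and SES-CD they do not. The first sentence of 3.1 points to the last feeder colonoscopy, which comes after feeder treatment, and SAP 6.1 points to the value before it. SAP 11.0 does not list this as a change.

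On the SAP definition, every endoscopic change score is a sum of what happened in 1311.6 and what happened in this trial. The protocol says the yearly colonoscopies are there to assess continued treatment, yet no planned endpoint measures, within the same patients, how the scores moved after they entered the extension. A reader of the change table could take improvement gained in the feeder trial for improvement on long-term maintenance.

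The entry examination is also not defined uniquely. For a relapsed patient, 3.1 names the 1311.6 colonoscopy, done before the relapse, although a newer one between Visits 1 and 2 is required. A direct roll-over without a colonoscopy at E1 or E5 also has one between Visits 1 and 2 (footnote 1 to Flow Charts 1 and 2).

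**Working it through.** **1. Which endpoints depend on the choice.** Let B0 be the score before the first 1311.6 dose, E the score at extension entry and V the score at an extension visit.

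- Dependent on the baseline: change and percentage change in CDEIS and SES-CD; 75% reduction (Protocol 5.1.1); SES-CD decrease of more than 50% (SAP 4.3.3); CDEIS response in isolated ileitis only (more than 50% reduction).
- Not dependent: CDEIS remission (4 or less; 2 or less in isolated ileitis), CDEIS response otherwise (7 or less), mucosal healing (no ulceration), deep remission (CDAI below 150 with CDEIS remission).

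**2. The identity.** V − B0 = (E − B0) + (V − E). The SAP reports the left side. The effect of continued treatment is in the last term.

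**3. Illustrations.** The documents give no endoscopic means or SDs, so all scores here are assumed.

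- CDEIS 14, 5, 8: from B0, 8 − 14 = −6 (6/14 = 43% better); from E, 8 − 5 = +3 (3/5 = 60% worse).
- SES-CD 20, 4, 9: from B0, −11 (55% lower, so still a decrease of more than 50%); from E, +5 (125% higher).
- CDEIS 16, 2, 4: from B0, −12 (75% lower, so still a 75% reduction); from E, +2 (100% higher).

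**4. Room for worsening in the relative criteria.** If the entry score is a fraction r below B0, then E = (1 − r)·B0. The decrease of more than 50% is kept while V stays below 0.5·B0, that is, up to a rise from entry of 0.5/(1 − r) − 1. For a 75% reduction the limit is 0.25/(1 − r) − 1.

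| Assumed r at entry | Rise before the >50% decrease is lost | Rise before the 75% reduction is lost |
|---|---|---|
| 60% | 25% | not met at entry |
| 75% | 100% | 0% |
| 80% | 150% | 25% |
| 90% | 400% | 150% |

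**5. Whether the Week 0 row in SAP Table 2 closes the gap.** Table 2 has a CDEIS and SES-CD row for Week 0, and SAP 12.9 evaluates deep remission there, so an entry value is intended. Two things limit it.

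- *Different patients at different visits.* SAP 9.1.2 imputes categorical endpoints only, so mean changes use whoever has data. Protocol 3.3.4.1 also stops treatment for endoscopically confirmed lack of efficacy. Take two assumed patients: A scores 12, 4, 8; B scores 12, 8 and has no Week 104 colonoscopy. Mean change from B0 is (−8 − 4)/2 = −6 at Week 0 and −4 at Week 104, an apparent worsening of 2. The only patient seen at both visits worsened by 4.
- *Week 0 may be empty.* Footnote 2 to the flow charts says assessments done at the last feeder visit need not be repeated, so the entry colonoscopy of a direct roll-over may exist only as feeder data. Note e to SAP Tables 4 and 5 handles this for fecal calprotectin and hs-CRP by combining the two studies. Table 2 has no such note.

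**6. Flow Chart 3 patients.** Table 2 counts days from the first s.c. dose, and the Week 0 window is open backwards to day −999. For these patients the Week 0 colonoscopy is therefore the one taken before i.v. re-induction. Change from it includes the re-induction effect and should not be pooled with that of direct roll-overs.

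**The case against.** The strongest reply is that this is a matter of wording. The sentence after the first statement in 3.1 says who needs a screening colonoscopy, so the first statement may only identify which examination counts as the entry one. SAP 6.1 then gives the analyst a single instruction. A feeder baseline is a legitimate choice for cumulative effect. The primary objective is safety, and all efficacy analysis is descriptive, so no error rate or sample size is involved. This stands, and it keeps the point at the level of clarification plus one added summary. But 3.1 does use the word baseline, does not separate the two uses, and leaves change scores outside the sentence on response.

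Several stronger inferences are tempting, and the documents do not support them:

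- *That the plan hides endoscopic worsening or leaves the stated aim unanswered.* The aim names endoscopic response and mucosal healing, and both are summarised by visit. Outside isolated ileitis, the 14, 5, 8 patient is a CDEIS responder at entry (5 is within 7) and a non-responder at Week 104 (8 is not), so the loss is recorded. If Week 0 is filled, the by-visit changes read −9 and then −6.
- *That the two references give different response results.* Neither document measures response from entry. Both tie it to the 1311.6 baseline, including in isolated ileitis.
- *That most of the change is already present at entry because entrants are responders.* Entry is selected on CDAI, and Protocol 1.1 itself notes poor correlation between CDAI and CDEIS.
- *That relapsed patients get a wrong change score.* Under SAP 6.1, neither the last feeder colonoscopy nor the one between Visits 1 and 2 is the baseline for change.

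**Conclusion.** The concern holds in a limited form. The current text of the protocol and SAP names different endoscopic baselines for change in CDEIS and SES-CD. On the SAP definition, change and relative-reduction criteria combine feeder-trial and extension change, and nothing planned reports the extension part in the same patients. The Week 0 row is a partial remedy only.

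The direction follows from the identity and needs no assumption. The size does: the illustrations and the table of allowable worsening rest on assumed scores, and the documents do not show how much change is present at entry. The absolute endoscopic endpoints and the safety analyses are untouched. The change is worth making, but the planned analysis is not invalid without it.

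**What to change.** 1. **Protocol 3.1 and SAP 6.1.** State that the last value before the first 1311.6 dose is the baseline for all response and change endpoints. In 3.1, replace the baseline label on the last feeder colonoscopy with a separate term, for example *extension-entry value*: the last colonoscopy before the first M15-989 dose, which is the one between Visits 1 and 2 where performed.
2. **SAP 9.3.** Beside change from feeder baseline, add change in CDEIS and SES-CD from the extension-entry value, by visit, in patients with both values. Give the number of pairs at each visit. Show Flow Chart 3 patients separately.
3. **SAP Table 2.** Add the rule in note e of Tables 4 and 5, so that feeder-trial colonoscopy data can fill Week 0.

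The cost is a few sentences and one extra descriptive table from data already collected, with no further colonoscopies. Reported endoscopic change may look less favourable. Pairing also does not recover patients without a later colonoscopy; it only ensures that the same patients are compared.

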3.1.1 Administrative structure of the trial

The trial is sponsored by AbbVie, Inc.

A Co-ordinating Investigator will be nominated to coordinate investigators at different sites participating in this multicentre trial. Tasks and responsibilities for the Co-ordinating Investigators will be defined in a contract filed before initiation of the trial.

Documents on participating (Principal) investigators and other important participants, especially their curricula vitae, will be filed in the CTMF.

All documentation collected during the trial and filed in the CTMF will be transitioned to AbbVie, Inc.

Details of the trial supplies including responsible institutions are given in [Section 4](#) of this protocol.

Details regarding Interactive Response Tool (IRT) used in this trial are provided in the ISF.

Details regarding procedures pertaining to central laboratory will be provided in the Laboratory Manual in ISF.

External vendors will be contracted to centrally manage videotapes of ileocolonoscopies. Details regarding the procedures pertaining to the central image managing system will be provided in the ISF.

The Investigator Site File (ISF) will be maintained at the sites as required by local regulations. A copy of the ISF documents will be kept as an electronic CTMF document and the CTMF will be transitioned to AbbVie, Inc.

3.1.1.1 Data Monitoring Committee (DMC)

The study will have a DMC independent from the sponsor. The purpose of the DMC is to ensure that the welfare of patients participating in this trial is maintained by:

- Monitoring the trial for possible untoward harmful effects or unexpected frequency of adverse safety events of study drugs;
- Assessing whether the goals of the trial are quite unlikely to be achieved, based on emerging data.

The DMC will perform an evaluation of the accrued patient data in order to recommend whether the trial or program should continue, be modified or stopped for safety concerns or ethical reasons. The DMC will review pertinent trial data, including deaths, SAEs and AEs, laboratory data and efficacy. All materials provided to the DMC are confidential. The tasks and responsibilities of the DMC will be filed in a contract before initiation of the trial and will contain written operating procedures. The DMC will maintain written records of all its meetings. Sponsor will remain blinded to these ongoing data reviews.

Details on the DMC, including the analyses, the composition of the DMC, the procedures, roles, responsibilities and regular meeting planner are provided in the DMC charter in the Investigator Site File (ISF).

3.2 DISCUSSION OF TRIAL DESIGN, INCLUDING THE CHOICE OF CONTROL GROUP(S)

Study 1311.20/M15-989 is designed as an open label, single group trial and is expected to generate long term safety information to support the submission for registration. As noted in [Section 4.1.3](#) below, the s.c. dose (180 mg every 8 weeks) from the study 1311.6 will be used in all patients for the maintenance treatment. Since study 1311.6 has not been completed and analysed at the time this study has been designed, the highest induction schedule of three 600 mg infusions every 4 weeks that was found safe in 1311.6 will serve as re-induction dose for patients who lost their response or remission between completion of 1311.6 and enrolment in 1311.20/M15-989.

The goal of this study is to obtain initial on-drug, long-term safety data together with early evidence on the durability of the clinical response, that both will be essential for the licensing authorization application. As typical for an open-label, single-group study, neither powered nor controlled analyses can be obtained. However, the study may yield initial tendencies and at the same time permit early study participants to continue a successful therapy.

3.3 SELECTION OF TRIAL POPULATION

Eligible patients from preceding 1311.6 trial will be offered participation in this long term extension trial based on their achievement of clinical response. The check for patient eligibility will be based upon a successful treatment ([Section 3.3.2](#)) of the preceding trial and on signing the Informed Consent for the long term extension trial.

Based on the results for the MEDI-2070 compound with identical mode-of-action, it is expected that up to 50 % of patients in 1311.6 will achieve a clinical response after induction treatment. Assuming a 100% maintenance rate of their response, up to 60 patients may be entered in this trial.

A log of all patients included into the study (i.e. having given informed consent) will be maintained in the ISF at the investigational site irrespective of whether they have been treated with investigational drug or not.

3.3.1 Main diagnosis for study entry

3.3.2 Inclusion criteria

1. Patients with Crohn's disease, who have successfully completed the preceding trial 1311.6. Successful treatment is defined as:
 - Completion of period 2 in 1311.6 with a clinical response (drop in CDAI from baseline by ≥ 100) but no remission (CDAI < 150) at Visit E1; or
 - Completion of period 3 in 1311.6 with a clinical response (drop in CDAI from baseline by ≥ 100) **and** / or remission (CDAI < 150) at Visit E5; or
 - Completion of period 2 or 3 in 1311.6 per protocol with a clinical response or remission before initiation of 1311.20/M15-989 may roll-over either directly if that response/remission is maintained or through an open-label i.v. re-induction phase if they have lost their previous response/remission.(for more details see Section 3.1)

2. Female patients:
 - a. Women of childbearing potential (not surgically sterilized and between menarche and 1 year postmenopause), that, if sexually active agree to use one of the appropriate medically accepted methods of birth control in addition to the consistent and correct use of a condom from date of screening until 20 weeks after last administration of study medication. Medically accepted methods of contraception are: ethinyl estradiol containing contraceptives, diaphragm with spermicide substance, and intra-uterine-device, or
 - b. Surgically sterilized female patients with documentation of prior hysterectomy, tubal ligation or complete bilateral oophorectomy, or
 - c. Postmenopausal women with postmenopausal is defined as permanent cessation \geq 1 year of previously occurring menses, and
 - d. Negative serum β -Human Chorionic Gonadotrophin (β -HCG) test at screening and urine pregnancy test prior to randomization.
- Male patients:
 - a. Who are documented to be sterile, or
 - b. Who consistently and correctly use effective method of contraception (i.e., condoms) during the study and 20-weeks after last administration of study medication.
3. Be able to adhere to the study visit schedule and other protocol requirements.

